6.8. Other Safety: Body Weight, BMI, Breast Imaging and Pregnancies

Bodyweight

Bodyweight is assessed at Screening, Day 1, Day 85, and Day 169, as well as the ET visit where applicable. Height is assessed once at the screening visit.

The observed bodyweight and BMI values at each visit, along with the change from baseline to each post-baseline visit will be summarized descriptively as continuous variables by treatment group and overall. The following categorizations will additionally be summarized for body weight at each visit:

Category	Change from Baseline
Category 1	≥ 10% loss
Category 2	≥ 5 - 10% loss
Category 3	-5% < Weight change <+5%
Category 4	≥ 5 - 10% increase
Category 5	≥ 10% increase

Breast Imaging and Pregnancies

Breast imaging for female subjects is conducted at the screening visit and at the day 169 visit. Imaging is not required during the screening period if the subject has had a negative breast cancer imaging status (i.e., not considered clinically abnormal and/or requiring further evaluation/treatment) within 6 months prior to the screening visit. If clinically indicated, an ultrasound or MRI may also be conducted for breast cancer imaging, per the investigator's discretion. Summary statistics will be used to describe the breast imaging results.

6.9. Subgroup Analyses for Safety

The count and percentage of subjects who report at least one TEAE will be summarized by treatment group and PT for the subgroups outlined below.

- Sex (male, female)
- Race (White, Non-white)
- Age at baseline ($<65, \ge 65 \text{ years}$)
- Ethnicity (Hispanic or Latino, Not Hispanic or Latino)
- Geographic region (North America, Europe, South America, Asia)

- Slow vital capacity $(80\%, \ge 80\%)$
- Use of approved background therapy for ALS (Y/N)

7. PHARMACOKINETIC OUTCOMES

Approximately 36 subjects from selected sites will be enrolled in the PK sub-study.

- Blood samples for riluzole, edaravone, and/or sodium phenylbutyrate/taurursodiol PK will be collected at Day -28 predose (prior to the first dose of riluzole, edaravone, and/or sodium phenylbutyrate/taurursodiol on Day -28) and 1 hour (±15 minutes) post-dose.
- Blood samples for PTC857, riluzole, edaravone, and/or sodium phenylbutyrate/taurursodiol PK will be collected from those subjects taking part in the PK Sub-Study at predose (prior to the first dose of the day) and at 1, 2, 4, 5, 6, 8, and 12 hours (±15 minutes) (prior to the second dose) post-dose on Day 1 and Day 29.
- Blood samples for PTC857 PK only will be collected predose (prior to the first dose of the day) and at 1 hour (±15 minutes) and 4 hours (±1 hour) post-dose on Day 85, and predose only at all subsequent visits with blood PK sampling.
- CSF samples will be collected predose (first dose of the day) on the Baseline Visit, Day 29 Visit, and the End of Treatment Visit.

Summary statistics for plasma concentrations vs. time will be provided, in addition to by-subject listings.

PK data collected from this study will be included in non-compartmental analysis and Population PK analysis. Separate PK analysis plan(s) and report(s) will be provided.

9. PROGRAMMING CONSIDERATIONS

All tables, figures, listings (TFLs), and statistical analyses will be generated using SAS for Windows, Release 9.4 or higher (SAS Institute Inc., Cary, NC, USA). Computer-generated table, listing and figure output will adhere to the following specifications.

- 1. One SAS program can create several outputs.
- 2. Each output will be stored in a separate file.
- 3. Output files will be delivered in Word format.
- 4. The numbering of TFLs will follow ICH E3 guidance.
- 5. All tables and listings will be produced in landscape orientation. Figures use the orientation that best facilitates interpretation of the data.
- 6. All TFLs will be produced using the Courier New font, size 10. The smallest acceptable point size for the Regulatory Authorities is 8.
- 7. Headers and footers for figures will be in Courier New font, size 8, which is the smallest acceptable point size for the Regulatory Authorities.
- 8. TFLs will be in black and white (no color), unless otherwise specified.
- 9. Specialized text styles, such as bolding, italics, borders, shading, and color are not used in the tables and listings, unless otherwise specified. Color may be used in figures containing multiple plotted lines as long as information is not lost when the figure is reproduced in monotone.
- 10. A mixed case will be used for titles, footnotes, column headers, and programmer-supplied formats, as appropriate.
- 11. For categorical parameters, all categories will be presented in the table, even if n=0 for all treatment groups in each category. For example, the frequency distribution for symptom severity would appear as:

Severity Rating	n
Mild	2
Moderate	5
Severe	0

- An Unknown or Missing category will be added to each parameter for which information is not available for 1 or more subjects.
- Unless otherwise specified, the estimated mean, median, Q1 and Q3 for a set of values will be printed out to 1 more significant digit than the original values, and standard deviations and standard errors will be printed out to 2 more significant digits than the original values. The minimum and maximum will report the same significant digits as the original values.
- Confidence intervals are displayed within round brackets and separated by a comma. The lower limit is presented first, and the upper limit is presented second. The confidence interval is placed either beside or below the corresponding estimate. The estimate and the confidence limits are presented using the same degree of precision.

- P-values will be output in the format: '0.xxx', where xxx is the value rounded to 3 decimal places. Every p-value less than 0.001 will be presented as <0.001. If the p-value is returned as >0.999, then present as >0.999.
- Percentage values will be printed to one decimal place. Unless otherwise noted, for all percentages, the number of subjects in the analysis population for the treatment group who have an observation will be the denominator. Percentages after zero counts will not be displayed and percentages equating to 100% will be presented as 100%, without decimal places.
- Tabular display of data for medical history, prior/concomitant medications, and all tabular displays of adverse event data will be presented by the body system, treatment class, or SOC with the highest occurrence in the active treatment group in decreasing order, assuming all terms are coded. Within the body system, drug class and SOC, medical history (by preferred term), drugs (Medication class), and adverse events (by preferred term) will be displayed in decreasing order. If incidence for more than 1 term is identical, they will then be sorted alphabetically.
- Missing descriptive statistics or p-values which cannot be estimated will be reported
 as '-' Missing values for numeric and character variables are displayed as blanks in
 data listings.
- The percentage of subjects will normally be calculated as a proportion of the number of subjects assessed in the relevant treatment group (or overall) for the analysis population presented. However, careful consideration is required in many instances due to the complicated nature of selecting the denominator, usually the appropriate number of subjects exposed. Details will be described in footnotes or programming notes, as necessary.
- If no relevant data are available at all for a display, then present "No data to Report".

10. MOCK TABLES, LISTINGS, AND GRAPHS

The study tables, listings and graphs shells will be provided in a separate document.

11. APPENDIX 1: SCHEDULE OF ASSESSMENTS

Schedule of Assessments for Screening and Double-Blind Treatment Period (Part A)

							ent Period 4 W)				EOS/ FU	Early Termination
		Day -28 (±3)	Day 1 (-3) ^a	Day 14 (±3)	Day 29 (±3)	Day 57 (±3)	Day 85 (±3)	Day 113 (±3)	Day 141 (±3)	Day 169 (±3)	Day 197 (±3)	Ī
			Baselinea							End of Treatment ^b	Follow- Up ^c	ET₫
Telephone call/in-home or in-person visit ^f	IP	PC	IP	PC/IH	PC/IH ^{e,f}	PC/IH ^f	IP	PC/IH ^f	PC/IH ^f	IP	PC	IP
COVID-19 PCR	X											
Informed consent	X						Χg			Xh		
Inclusion/exclusion criteria	X											
Re-evaluation eligibility			X									
Randomization			X									
Height	X											
Weight and BMI	Х		X				X			Х		X
Demographics	X											
Medical history	X											
Serum/urine pregnancy test (females only) ^I	Х		Х		Х	Х	X	Х	Х	Х	X	Х
FSH measurement	X											
12-Lead ECG ^k	X		X				X			X		Х
Vital signs	X		X		X	Х	X	X	Х	X		Х
Physical exam ^m	X		X				Х			X		X
Sparse PK blood sampling ⁿ			Х				X			Х		Х
Clinical laboratory tests ^o	Х		X	Xp	X	X	X			X		X
CSF for biomarkers ^{q,r}			X							X		X
Laboratory biomarkers (blood and urine) ⁶			Х				X			Х		Х
ALSFRS-R ^t	X	X	X		X	Х	X	X	X	X	X	X
PFTsu	X		X				X			X		X
ALS CBS	X		X				X			X		Х
Modified Norris Scale			X				X			X		X
ALSAQ-40			X				X			X		X
EQ-5D-5L			X				X			X		X
C-SSRS ^V	X	Х	X		X	Х	X	X	X	X	X	X
Study drug dispensation			X				X					
Adverse events	X	Х	X	Х	X	Х	X	X	Х	X	Х	Х
Prior/concomitant medications	X	X	X	X	X	X	X	X	X	X	X	X
Mammogramw	X							İ		X		Xx

							ent Period 4 W)				EOS/ FU	Early Termination
Study Day	Screening (-56 Days) (±5)	Day -28 (±3)	Day 1 (-3)*	Day 14 (±3)	Day 29 (±3)	Day 57 (±3)	Day 85 (±3)	Day 113 (±3)	Day 141 (±3)	Day 169 (±3)	Day 197 (±3)	
			Baseline*							End of Treatment ^b	Follow- Up ^o	ET ^d
				PK S	ub-Study /	ssessmen	tsy	•		•		
Telephone call or in- person visit	IP	IP	IP	PC/IH	IP	PC/IH	IP	PC	PC	IP	PC	IP
Serial PTC857 PK blood sampling			X		Х		Х			X		X
Riluzole PK blood sampling		Х	X		Х							
Edaravone PK blood sampling		Х	Х		Х							
Sodium phenylbutyrate/taurursod iol PK sampling		Х	X		X							
CSF for PK ²			X		X					X		X
Additional ECGs			X		X							

Abbreviations: ALS, amyotrophic lateral sclerosis; ALS CBS, ALS Cognitive Behavioral Screen; ALSAQ-40, ALS ASsessment Questionnaire; ALSFRS-R, ALS Functional Rating Scale-Revised; BMI, body mass index; COVID-19, coronavirus disease 2019; CSF, cerebrospinal fluid; C-SSRS, Columbia-Suicide Severity Rating Scale; ECG, electrocardiogram; EOS, end of study; EQ-5D-5L, five-level European quality of life five-dimensional questionnaire; ET, early termination; FSH, follicle-stimulating hormone; FU, follow-up; ICF, Informed Consent Form; IH, in-home; IP, in-person; LTE, Long-Term Extension; p75NTR, p75 neurotrophin receptor; PC, telephone call; PCR, polymerase chain reaction; PFT, pulmonary function test; PI, Principal Investigator; PK, pharmacokinetic; SAE, serious adverse event

- a The Baseline Visit will be defined as Day 1 of the study. Baseline Visit procedures may be performed within the 3 days before the day that study drug is first administered. The day in which the first dose of study drug is administered will be Day 1. For subjects taking part in the PK Sub-Study, the PK laboratory tests must be completed on the same day as the first dose of study drug.

 b Day 169 will be considered the End of Treatment Visit only for those who choose not to enter the LTE Period (Part B).

 c Follow-up Visit on Day 197 only for subjects who choose not to enter the LTE Period (Part B).

- d For subjects who terminate early from the study and consent to continued follow-up, the investigator should attempt to gain vital status on the participant and conduct the ALSFRS-R assessment approximately every 28 days for the remaining duration of the study, in accordance with local requirements/regulations.

 The Day 29 Visit will be conducted in-person for subjects participating in the PK Sub-Study only.

 For the telephone call/in-home visits, where applicable, the ALSFRS-R, C-SSRS, adverse events, and prior/concomitant medications assessments will be
- conducted via a telephone call. Vital signs assessments and samples for clinical laboratory tests will be collected via a home health nurse during applicable inhome visits at the subject's home during these visits. Subjects may go to the site for an in-person visit at the discretion of the PI. Visits indicated as in-person only may be conducted remotely (ie, in-home) following discussion between the site and the medical monitor. In-person visits that are conducted remotely must include have be conducted remotely (let, in-notine) following discussion between the site and the inequation inclined in in-persion risks that are conducted remotely first include the following assessments, at minimum (if such assessments are typically included during the visit): serum/urine pregnancy test (females only), vital signs, clinical laboratory tests, ALSFRS-R, C-SSRS, adverse events, prior/concomitant medications, sparse PK blood sampling, laboratory biomarkers, and ALSAQ-40.

 The ICF for Part B should be provided to the subject at the Day 85 visit to allow the subject adequate time to consider transitioning into Part B.

 The ICF for Part B should be signed by the subject at the Day 169 visit if they choose to enroll into Part B.
- Women of childbearing potential will have a serum pregnancy test at the initial Screening Visit and then undergo monthly urine pregnancy testing starting from Day 1 prior to randomization through the Follow-up Visit. If a urine pregnancy test is positive, a serum pregnancy test will be conducted for confirmation and dosing should be immediately suspended and evaluated for continued study participation based upon the result of the serum pregnancy test and in discussion with the

medical monitor. For months where an on-site visit is not scheduled, subjects will complete a urine pregnancy test at home, if local requirements allow, to be reported to the investigator and documented in the eCRF

- Postmenopausal female subjects only.
- * Sign to pausar remains subjects only.

 * Single 12-lead ECG measurements will always be performed prior to the dose of medication administered at the clinic. Subjects should be resting for at least 5 minutes in supine position prior to 12-lead ECG procedures.
- Trimites in supire position prior to 2-least 20-b procedures.

 1 Vital signs will consist of measurements of supine blood pressure, heart rate, body temperature, and respiratory rate. Vital sign measurements will be collected after the subject has been resting for 5 minutes. Blood pressure and heart rate measurements will be performed with subjects in a supine position, except when they semi reclined because of study procedures and/or AEs (eg, nausea, dizziness) or if deemed necessary by the PI or designee
- m A full physical examination will be completed during Screening Period. A targeted physical examination, including neurological examination, will be completed at
- all other timepoints.

 Blood samples for PK evaluation will be collected from all subjects not participating in the PK Sub-Study at predose (prior to the first dose of the day) and at 1 hour (±15 minutes) and 4 hours (±1 hour) post-dose on Day 1 and Day 85. The first 36 subjects that enroll in the study will have a 6-hour (±1 hour) post-dose on Day 1 and Day 85. The first 36 subjects that enroll in the study will have a 6-hour (±1 hour) post-dose on Day 1 and Day 85. The first 36 subjects that enroll in the study will have a 6-hour (±1 hour) post-dose on Day 1 and Day 85. The first 36 subjects that enroll in the study will have a 6-hour (±1 hour) post-dose on Day 1 and Day 85. The first 36 subjects that enroll in the study will have a 6-hour (±1 hour) post-dose on Day 1 and Day 85. The first 36 subjects that enroll in the study will have a 6-hour (±1 hour) post-dose on Day 1 and Day 85. The first 36 subjects that enroll in the study will have a 6-hour (±1 hour) post-dose on Day 1 and Day 85. The first 36 subjects that enroll in the study will have a 6-hour (±1 hour) post-dose on Day 1 and Day 85. The first 36 subjects that enroll in the study will have a 6-hour (±1 hour) post-dose on Day 1 and Day 85. The first 36 subjects that enroll in the study will have a 6-hour (±1 hour) post-dose on Day 1 and Day 85. The first 36 subjects that enroll in the study will have a 6-hour enroll in the study will hav blood sampling on Day 1 and Day 85; this 6-hour post-dose blood sampling must be at least 2 hours following the 4-hour post-dose blood sampling. Subjects enrolled after the first 36 subjects may optionally have the 6-hour (±1 hour) post-dose blood sampling on Day 1 and Day 85, if feasible. Time of last dose of study drug prior to the study visit should be recorded. On all other visits with blood samples for PTC857 PK, blood samples will only be collected predose. If any SAEs are observed, ad hoc PK sample(s) may be collected, if possible, to measure the levels of PTC857, riluzole, edaravone, and/or sodium phenylbutyrate/taurursodiol to determine the causality
- Clinical laboratory tests will consist of fasting lipid profile, hematology, coagulation, blood chemistry, and urinalysis. Urinalysis will only be performed at in-person clinic visits (ie, Screening, Day 1, Day 85, and Day 169).
 Clinical laboratory tests on Day 14 will consist only of a fasting lipid profile. Hematology and blood chemistry will not be evaluated during this visit.
- 1 It is the intention of the protocol that all subjects will consent to undergo lumbar punctures. Cerebrospinal fluid samples for biomarkers and PK will be collected at predose (first dose of the day) on both the Baseline Visit and the Day 169 Visit, lumbar punctures on these days may be conducted up to 5 days prior to the
- Baseline Visit and the Day 169 Visit. CSF biomarkers will be assessed as listed in Section 7.1.7.

 The lumbar puncture that is required may be skipped for an individual subject if the PI deems it appropriate, and after discussion with the medical monitor.

 Laboratory (blood and urine) biomarkers (aligned with the timing for the clinical laboratory tests) as per Section 7.1.7. Urine creatinine should be tested when urine p75NTR is sampled.
- The ALSFRS-R assessment must be performed by a certified rater.
- "Pulmonary function tests will assess slow vital capacity and Sniff Nasal Inspiratory Pressure. Forced vital capacity, vital capacity, forced expiratory volume, and maximum inspiratory pressure will not be measured. Refer to the laboratory manual for specific requirements at Screening. Oxygen saturation, respiratory rate, and heart rate will be assessed in both upright and supine positions. The Sniff Nasal Inspiratory Pressure test will assess nasal pressure in each unilaterally occluded nostril during a maximal sniff to assess inspiratory muscle strength.

 * During the Screening Visit (Day -56), the "baseline" version of the C-SSRS will be administered. At all other visits, the "since last visit" version will be
- Wammograms to be conducted for female subjects only. A mammogram is not required during the Screening Period if the subject has had a negative breast cancer imaging status (ie, not considered clinically abnormal and/or requiring further evaluation/treatment) within 6 months prior to the Screening Visit. If clinically indicated, an ultrasound or MRI may also be conducted for breast cancer imaging, per the investigator's discretion. If a subject cannot complete the Screening mammogram or any necessary follow-up procedures during the Screening Period, the Screening Period may be extended after discussion and agreement with the medical monitor.
- x Women who have been exposed to study drug for at least 3 months and discontinue treatment before reaching the Day 169 Visit will have breast cancer surveillance imaging performed at the Early Termination Visit. Women who have been exposed to study drug for <3 months and discontinue treatment before reaching the Day 169 Visit may have breast cancer surveillance imaging performed at the investigator's discretion.

 The following additional procedures will be conducted only in subjects taking part in the optional PK Sub-Study:

 Blood samples for riluzole, edaravone, and/or sodium phenylbutyrate/taurursodiol PK will be collected at Day -28 predose (prior to the first dose of riluzole,
- - edaravone, and/or sodium phenylbutyrate/taurursodiol on Day -28) and 1 hour (±15 minutes) post-dose. Subjects should be instructed not to take riluzole, edaravone, and/or sodium phenylbutyrate/taurursodiol on Day -28 prior to the study visit.
 - Blood samples for PTC857, riluzole, edaravone, and/or sodium phenylbutyrate/taurursodiol PK will be collected from those subjects taking part in the PK Sub-Study at predose (prior to the first dose of the day) and at 1, 2, 4, 5, 6, 8, and 12 hours (±15 minutes) (prior to the second dose) post-dose on Day 1 and Day 29. Blood samples for PTC857 PK only will be collected predose (prior to the first dose of the day) and at 1 hour (±15 minutes) and 4 hours (±1 hour) post-dose on Day 85, and predose only at all subsequent visits with blood PK sampling. Subjects should be instructed not to take riluzole, edaravone, and/or sodium phenylbutyrate/taurursodiol on Day 1 or Day 29 prior to the study visit. Time of last dose of study drug and riluzole, edaravone, and/or sodium
 - phenylbutyrate/taurursodiol prior to the study visit should be recorded.

 Additional samples of predose (trough) CSF will be collected for PK evaluation at all lumbar puncture timepoints.
- Additional ECG measurements will be performed at the time of the 4-hour and 8-hour post-dose PK samples (±15 minutes from PK sample blood draw).

 The lumbar punctures for CSF collection in the PK Sub-Study may occur within 5 days prior to or after the scheduled visit day.

Schedule of Assessments for Long-Term Extension Period (Part B)

Schedule of Assessments for Continued Long-Term Extension Period (Part C)

Day and month missing, year present	 Year different to year of first study drug dose: Impute day and month with "01JAN". Year same as year of first study drug dose: Impute month and day with same month and day as first dose of study drug. 	Impute day and month with "31DEC"

Partial Missing	Imputation for Start Date	Imputation for Stop
Start or Stop Date		Date
Month missing, day	Year different to year of first study drug dose:	Impute with "DEC"
and year present	Impute month with "JAN".	
	Year same as year of first study drug dose: Impute	
	month with same month as first dose of study drug.	
Caveats	If any imputed start date leads to a start date that is af	ter the stop date, then
	the start date will be imputed with the date of the stop	of AE.

ALSFRS-R incomplete / missing data

This section describes visit level imputations performed prior to the multiple imputation procedure.

If 1 item is missing within a domain (e.g. Bulbar), then the domain item will be inputted using the following formula:

Imputed domain score = mean of non-missing items multiplied by 3.

If item 12 on the ALSFRS score is missing, and the patient is not reported as having received non-invasive ventilation at the time of the visit (concomitant procedures CRFs) then item 12 will be imputed as a 4.

Total Score:

If a whole domain is missing or two items are missing, then the total ALSFRS-R total score will be imputed from the remaining 3 domains as the mean of all answered item scores in the 3 domains x 12. Total score will not be imputed if more than 1 domain has 2 or more missing items.

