3.2.7. ALS Functional Rating Scale - Revised (ALSFRS-R) score

The ALSFRS-R is a quickly administered (5-minute) ordinal rating scale that assesses the subjects' capability and independence in 12 functional activities across 4 subdomains of bodily function (bulbar, gross motor, fine motor, and respiratory) relevant in ALS. Each activity is recorded to the closest approximation from a list of 5 choices, scored 0 (total loss of function) to 4 (no loss of function), with the total score ranging from 0 to 48 and higher scores indicating less functional impairment (Cedarbaum 1999).

The score change from baseline will be calculated as the post baseline score minus the baseline score, so that a positive score for change from baseline would indicate improvement in function relative to baseline, while a negative score indicates worsened disease relative to baseline.

Subdomains	Items
Bulbar	Speech, Salivation and Swallowing
Fine Motor	Handwriting, Cutting Food/Handling Utensils and Dressing Hygiene
Gross Motor	Turning in Bed, Walking and Climbing Stairs
Respiratory	Dyspnea, Orthopnea and Respiratory Insufficiency
Scores for each ite rating)	em range from 0 to 4 (0 representing the worst/lowest functional rating and 4 the best

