3.3. Estimands

3.3.1. Estimand for Primary Efficacy (Combined Assessment of Function and Survival)

Research Question: What is the improvement in combined survival and activities of daily function between subjects treated with PTC857 versus Placebo after 24-weeks, in the population of patients with ALS as defined by the study's inclusion exclusion criteria, regardless of whether subjects complete their assigned treatment during the 24-week treatment period, or underwent a tracheostomy, or had permanent assisted ventilation?

Patient Population: All subjects who are randomized to a treatment assignment and take at least 1 dose of study drug during the double-blind treatment period, and who have a decrease in the ALSFRS-R score of ≤ 4 points during the Screening Period (ITT1 Population).

Endpoint: CAFS rank at Week 24

Population-level summary: Difference in the mean CAFS rank at Week 24 between PTC857 and Placebo.

Treatment Condition: PTC857 compared to Placebo, in the setting where patients have the option (at screening), to take SOC treatments for ALS that are approved in their country; patients are allowed to take either edaravone or sodium phenylbutyrate/taurursodiol as monotherapy or in combination with riluzole but not in combination with each other.

Intercurrent Event Strategy:

- 1. The intercurrent event of death will be accounted for as part of the composite CAFS score.
- 2. Treatment Discontinuation: Data collected after treatment discontinuation will be included and analyzed according to the treatment group to which the participant was randomized. (Treatment Policy).
- 3. Initiation of new therapy for ALS: If subjects initiate new additional therapy for ALS after randomization their data will be analyzed according to the treatment group to which the participant was randomized, i.e., regardless of the initiation of new therapy for ALS. (Treatment Policy).
- 4. Tracheostomy: Data collected after a Tracheostomy will be included and analyzed according to the treatment group to which the participant was randomized. (Treatment Policy).
- 5. Permanent Assisted Ventilation (PAV): Data collected after a PAV will be included and analyzed according to the treatment group to which the participant was randomized. (Treatment Policy).

The same estimand framework (above) will be used to analyze the primary endpoint for the ITT2 population.

3.3.2. Estimands for Change from Baseline in ALSFRS-R at Week 24

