15. APPENDIX 5. MAPPING ALSFRS-R TO KING'S STAGE

The King's clinical staging criteria for ALS (Balendra 2014) is defined as a count of involved central nervous system (CNS) regions (Stage 1, 2 or 3), requirement for gastrostomy or noninvasive ventilation (Stage 4) and death (Stage 5).

Stage	Definition
1	Functional involvement of one CNS region (symptom onset)
2	Functional involvement of two CNS regions
3	Functional involvement of three CNS regions
4	Need for gastrostomy (4A) or non-invasive ventilation (4B)
5	Death

- 1. Bulbar region is involved: If the subject dropped any points on any of the three ALSFRS-R questions regarding speech (question 1), salivation (question 2) or swallowing (question 3).
- 2. Upper limb region is involved: If the subject dropped any points on either of the two ALSFRS-R questions regarding hand function, which are handwriting (question 4) and ability to cut food and handle utensils (question 5A).
- 3. Lower limb region is involved: If the subject dropped any points on the ALSFRS-R question regarding ability to walk (question 8).
- 4. Stage 4A attained: If question 5B is answered instead of question 5A, which is only answered by patients without a gastrostomy.
- 5. Stage 4B reached: If a patient scored 0 points on question 10 or less than 4 points on question 12.

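### The rule for a missing ALSFRS-R item 12 checks only for non-invasive ventilation, so read literally it gives an invasively ventilated patient that item's best score

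*SAP*

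**What the plan says.** Three rules in the Part A SAP bear on this.

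- **Item 12 rule (Section 12, Appendix 2).** For a missing item 12 in a patient not on record as "having received non-invasive ventilation at the time of the visit (concomitant procedures CRFs) then item 12 will be imputed as a 4". Non-invasive ventilation is the only condition tested. Appendix 2 of the Parts B/C SAP has the same sentence.
- **General rule for one missing item (same appendix).** "Imputed domain score = mean of non-missing items multiplied by 3". A missing item 12 with items 10 and 11 present meets this rule too, and nothing says which prevails.
- **Timing (same appendix).** "This section describes visit level imputations performed prior to the multiple imputation procedure".

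Section 3.2.7 says each item is "scored 0 (total loss of function) to 4 (no loss of function"), and lists the respiratory items as "Dyspnea, Orthopnea and Respiratory Insufficiency".

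The SAP also provides for patients who go on to invasive support. Section 3.3.1 (primary estimand) states: "Data collected after a Tracheostomy will be included and analyzed according to the treatment group to which the participant was randomized". It treats permanent assisted ventilation in the same way, as does Section 3.3.2 for change in ALSFRS-R. Section 3.3.3.1 counts both as events, alongside death, in respiratory-support-free survival.

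**The concern.** The rule infers intact respiratory function from the absence of one kind of support. A patient on invasive ventilation need not have non-invasive ventilation recorded, so the inference fails for the patients in the worst respiratory state. The same SAP would count that state as a failure event in Section 3.3.3.1 and, if item 12 is blank, as no loss on the item in the ALSFRS-R total.

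Because the 4 is assigned before multiple imputation, it is identical in all 100 imputed datasets and carries no imputation uncertainty. The sensitivity analyses in Sections 5.2 to 5.4 and 5.5.1.3 vary the strata, the analysis set or the model for missing visits. None varies this rule.

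Four analyses are touched:

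- the functional part of CAFS, the primary endpoint;
- the ALSFRS-R MMRM, the first secondary test;
- the respiratory subdomain analysis (Section 5.5.1.1), where 4 points is a third of the 12-point range;
- the count of declines of 18 points or more at Week 24 (Section 6.2.3), which is meant to detect accelerated progression and where an overstated score can take a patient below the threshold.

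**Working it through.** **1. Error at one visit.** The rule assigns 4, the item maximum. The overstatement is 4 minus the true score: 1, 2, 3 or 4 points for a true score of 3, 2, 1 or 0. It is never negative. The documents give the 0 to 4 range but not the anchors of item 12, so a true score of 0 under invasive ventilation is an assumption.

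**2. Against the SAP's own proration rule.** Let a and b be items 10 and 11. Proration gives a respiratory domain score of 1.5(a + b). The item 12 rule gives a + b + 4. The difference is 4 − 0.5(a + b), which is never below zero.

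| Items 10 and 11, each | Proration | Item 12 rule | Difference |
|---|---|---|---|
| 0 | 0 | 4 | 4 |
| 1 | 3 | 6 | 3 |
| 2 | 6 | 8 | 2 |
| 3 | 9 | 10 | 1 |
| 4 | 12 | 12 | 0 |

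The choice between the two rules matters most where the other respiratory items are lowest.

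**3. The branch where non-invasive ventilation is recorded.** Only proration remains, and the implied item 12 is (a + b)/2. With both items at 4 it is 4. Appendix 5 assigns King's Stage 4B (non-invasive ventilation) as follows: "If a patient scored 0 points on question 10 or less than 4 points on question 12". Appendix 5 does not state the converse, that every patient on such support scores below 4, so this is a tension rather than a contradiction.

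**4. The planning figure, reproduced first.** Inputs from SAP Section 1.5: 205 and 102 subjects, difference 2 points, SD 5.3, two-sided 0.05, survival 96.5% and 95%, stated power about 85%.

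- Standard error = 5.3 × √(1/205 + 1/102) = 0.642. Power = Φ(2/0.642 − 1.96) = 87.6%.
- With the Wilcoxon efficiency of 0.955 (SD 5.3/√0.955), power is 86.1%.
- Simulating the joint rank test (deaths ranked lowest, t-test on ranks, no covariates, 8,000 runs) gives 86.1%.

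The stated figure is reproduced to within about a point.

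**5. Trial-level effect of the rule.** In the same simulation, the worst-ranked survivors in either arm were raised by 4 points. The shares are assumed, since the documents give none.

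| Share affected | Subjects of 307 | Power |
|---|---|---|
| 0% | 0 | 86.1% |
| 1% | 3 | 84.9% |
| 2% | 6 | 84.9% |
| 3% | 9 | 85.2% |

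The Monte Carlo standard error is √(0.86 × 0.14/8,000) = 0.4 points for each figure. A second simulation raised only placebo subjects, the direction that would hide a benefit. Power was 85.6% with none raised, 84.8% with one and 85.1% with three (standard error about 0.5). The loss is about 1 point or less and is hard to separate from simulation noise.

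**6. Why so little.** CAFS uses ranks, and affected patients are likely to be near the bottom already. The shift is 4/5.3 = 0.755 SD. From −2 SD it moves a patient to −1.245 SD, from about the 2nd to the 11th percentile. From −2.5 SD the move is from about the 1st to the 4th.

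**The case against.** The strongest objection is rarity. The rule acts wrongly only if the patient is alive, is invasively ventilated, has the scale administered, has item 12 blank and has no non-invasive ventilation recorded. Entry required an ALSFRS-R total of at least 34 and slow vital capacity of at least 60% (Protocol Section 4.2). ITT1 excludes losses above 4 points during screening. Certified raters score the scale, and it is not obvious why one would leave this item blank for a patient on a ventilator. CAFS compares Week 24 scores only, so earlier visits reach it only through the imputation model. The subdomain analysis is supplementary, with nominal p-values. All of this stands and keeps the trial-level effect small. It does not repair the rule: the SAP has a dedicated instruction for this item, so missing values are expected, and the instruction returns the wrong value when the conditions coincide.

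Three further limits also stand:

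- The documents do not define permanent assisted ventilation as invasive. If it is delivered and recorded as non-invasive ventilation, the patient is not given a 4. A reader might infer that every such patient is mis-scored; the text does not support that.
- If a programmer lets proration prevail, the 4 is not assigned. Taking the specific rule to override the general one is the natural reading, but it is a reading.
- The procedures CRF is not in the documents, so how ventilation is coded cannot be checked.

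A reader might also set 4 points beside the SD of 5.3 and conclude that a mid-ranked patient is carried well up the ranking. That measures the wrong patient, as step 6 of the working shows.

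**Conclusion.** The rule is wrong as written for a narrow group and should be corrected in both SAPs. On the natural reading of precedence, a patient with a tracheostomy or other invasive ventilation, item 12 missing and no non-invasive ventilation recorded is scored as having no loss on that item. That value is then analysed as observed data. The score is the best for one item, not for the respiratory domain, whose maximum is 12.

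The overstatement is 1 to 4 points per affected visit, with 4 resting on an assumed true score of 0. The 4-point case is twice the SAP's 2-point planning difference for that patient. At trial level the loss is about 1 power point or less, even with an assumed 1 to 3% of subjects affected, and the real share at 24 weeks is probably smaller. The documents therefore do not support inferring that the primary result is materially biased. Nor do they support the inference that a ventilated patient must be scored 0, because item 12's anchors are not given.

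**What to change.** Make the same change in Appendix 2 of both SAPs:

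1. Impute item 12 as 4 only if no ventilatory support of any kind is recorded on the procedures CRF as in use at the visit. Name non-invasive ventilation, tracheostomy, permanent assisted ventilation and other invasive ventilation.
2. Where any support is recorded, do not assign 4. Use the existing within-domain proration with the implied item 12 value kept below 4, in line with Appendix 5. Alternatively, use the scale's own anchor for invasive ventilation if the sponsor confirms it from the instrument. Proration is only a partial correction if the true score is 0: with items 10 and 11 both at 3 it gives 9, against 6.
3. State that the item 12 rule takes precedence over the general proration rule.

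The cost is a few sentences in each SAP and one programming condition on a CRF the rule already consults. The sponsor should first confirm that this CRF distinguishes the types of support and dates them well enough to match to visits. No new data collection or change in sample size is needed.
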